## **Statistics**

## **Primary Analysis Plan for efficacy**

The primary outcome measure is the median percentage change (across study subjects) in s MADRS from baseline to 1 month follow up. The significance of changes will be assessed using the non-parametric Wilcoxon signed-rank test; however, since this is a pilot study to determine effect sizes, demonstration of a significant effect is not a defined goal of the study.

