## Inclusion criteria - Individuals with MDD

*Participants will be men and women who:*

- Are aged 50 or older
- Able to read, write, and communicate in English
- Have a caregiver who is willing and able to provide the home tDCS sessions.
- Participants must be under the care of a treating psychiatrist who approves of the study participation and believes that TMS or ECT is indicated for his/her patient but that
  - it would not endanger the patient to participate in the present study rather than pursue such alternative, or
  - the patient could not gain access to TMS or ECT due to COVID-19

*(The depression phase of bi-polar disorder is not a reason for exclusion if the treating psychiatrist believes TMS or ECT would be indicated).*

Participants with MDD must fit into one of the following 3 groups (***medication-resistant MDD defined as 1) participant's condition has not responded to prescribed antidepressant medication; 2) participant is medication intolerant, or 3) some other underlying reason***):

- Patients with medication-resistant Major depressive disorder (MDD) who have undergone repetitive transcranial magnetic stimulation (rTMS) or electroconvulsive therapy (ECT) and responded to it but whose benefit has lapsed and they need repeat rTMS or ECT course that they cannot access;
- Patients with medication-resistant MDD who are undergoing rTMS or ECT and responding, but cannot continue to get the rTMS or ECT course due to COVID-19 pandemic-related regulations or other access concerns
- Patients with medication-resistant MDD who are referred to rTMS or ECT and are found well qualified but cannot access rTMS or ECT due to COVID-19 pandemic-related regulations or other access concerns.

Further, participants must:

- Meet criteria for a diagnosis of MDD according to the Diagnostic and Statistical Manual of Mental Disorders (DSM-IV-TR) (American Psychiatric Association, 2000), as determined via an tele-health interview with a study psychiatrist, and confirmed with the Mini International Neuropsychiatric Interview (MINI; Version 5.0.0) (Sheehan et al., 1998) and the prospective participant's primary psychiatrist.
- Currently experiencing a major depressive episode of at least four weeks' duration as part of a unipolar or bipolar depression. Score will need to be at least 20 on the MADRS.

Participant caregiver-administrators:

*Caregiver-administrators will be men and women, who may be a spouse, family member or friend who is*

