Wks 1-4, D 7, 14, 21, and 28	Weekly assessments	Participants with MDD only Week 1-4 Assessment completion (Day 7, 14,21, and 28); depression symptoms and quality of life assessments	Study research assistant	30 minutes	Phone
Home tDCS administration Treatment taper period – weeks 5-8 Participant ratings of suicidality will be completed each day, and responses will be monitored and immediately be reviewed in real time by the study RA and study psychiatrist. Any changes from baseline will result in an immediate contact to the participant by the study psychiatrist.					
Wk 5, D 30,32,34	Home-based tDCS Total of 3 sessions, one every other day over a 6 day period.	The caregiver-administrator will administer the in-home tDCS session with remote staff monitoring and video conferencing if necessary Daily diary	Study research assistant	1 hour	Participant's Home
Wk 6-7, D 37,40, 43	Home-based tDCS Total of 3 sessions, one every third day over a 9 day period	The caregiver-administrator will administer the in-home tDCS session with remote staff monitoring and video conferencing if necessary Daily diary	Study research assistant	1 hour	Participant's Home
Wk 8 D 47,51, 55	Home-based tDCS Total of 3 sessions, one every fourth day over a 12 day	The caregiver-administrator will administer the in-home tDCS session with remote staff monitoring and video conferencing if necessary Daily diary	Study research assistant	1 hour	Participant's Home

	period				
Wks 5-8 D35, 42, 49, 56	Weekly assessments	Participants with MDD only Weeks 5-8 Assessment completion (Day 35, 42,49, and 56); depression symptoms and quality of life assessments	Study research assistant	30 minutes	Phone
Home tDCS administration completed after Week 8, Day 55 session. Return of Home tDCS equipment to research team in the provided shipping materials and label.					
Four week follow-up period – weeks 9-12					
Wks 9- 12 D57-84	Four week follow-up period	Participants with MDD only The study research assistant will maintain weekly contact with the participant over the 4 week follow-up period	Study research assistant	20 minutes	Phone
Week 12, Day 84	Final study assessment	Both participants: Final assessment completion, depression symptoms, quality of life assessments, cognitive assessment	Study research assistant	1 hour	Phone
End of study: Results sent to participant with MDD and treating psychiatrist					

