## Statistical Methods and Analysis

### *Primary*

Feasibility and tolerability/safety will be evaluated using home-based data as it is collected by reported number of aborted sessions.

The *primary outcome* will be change in the observer rated MADRS score from baseline to the 1-month follow-up.

Clinical response is defined as  $\geq 50\%$  improvement in MADRS score from baseline to the 1-month follow-up. Remission is defined as a MADRS score  $\leq 10$ .

The *secondary outcome* measures will include the participant-rated Quick Inventory of Depressive Symptomatology (QIDS-SR) (Rush et al., 2003) and the Quality of Life Enjoyment and Satisfaction Questionnaire Short Form (Q-LES-Q-SF) (Endicott et al., 1993), both administered at the same time points as the MADRS. A computer-based cognitive test battery, CogState (<https://www.cogstate.com>), will provide an additional safety outcome measure. This battery includes tests designed to assess verbal learning and memory (International Shopping List Task), attention and psychomotor function (Detection Task), visual attention (Identification Task), visual learning and memory (One Card Learning Task), working memory (Two Back Task), and executive function (Set Shifting Task).

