## **Withdrawal and Stopping the study**

The criteria for discontinuing a participant's participation include the participant's request, as well as any unexpected life-threatening or potentially disabling event.

A study subject may be withdrawn from the study at any time if the study subject, the investigator, or the Sponsor feels that it is not in the study subject's best interest to continue.

All study subjects are free to withdraw from participation at any time, for any reason, specified or unspecified, and without prejudice.

Reasonable attempts will be made by the investigator to provide a reason for study subject withdrawals. The reason for the study subject's withdrawal from the study will be specified in the study subject's source documents.

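### The MADRS analysis uses only the baseline and 1-month values; if participants doing worse leave early, the pilot effect size is modestly overstated, and ratings already scheduled could correct for it

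*Combined protocol and SAP*

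**What the plan says.** - **Outcome and test.** Under Primary Analysis Plan for efficacy, the outcome is worded as "The primary outcome measure is the median percentage change (across study subjects) in s MADRS from baseline to 1 month follow up", and the test is then given as follows: "The significance of changes will be assessed using the non-parametric Wilcoxon signed-rank test". Statistical Methods and Analysis words the outcome as "change in the observer rated MADRS score from baseline to the 1-month follow-up", without the percentage. Response is an improvement of at least 50% to the same time point; remission is a MADRS of 10 or less.
- **Role of the analysis.** The plan calls the study a pilot to determine effect sizes and says that "demonstration of a significant effect is not a defined goal of the study".
- **Schedule.** Entry needs a baseline score: "Score will need to be at least 20 on the MADRS". The Visits table lists assessments of depression symptoms and quality of life on Days 7, 14, 21 and 28, then "Weeks 5-8 Assessment completion (Day 35, 42,49, and 56); depression symptoms and quality of life assessments", then a final assessment on Day 84. The table never names MADRS. Of the two self-rated questionnaires, QIDS-SR and Q-LES-Q-SF, the outcome section says "both administered at the same time points as the MADRS".
- **Leaving early.** Participation ends on request, "as well as any unexpected life-threatening or potentially disabling event". Under Stimulation Stopping criteria, stimulation stops on a clinician's view of substantial worsening or after more than 10 missed sessions. Participants are withdrawn for non-compliance or if continuing is judged unsafe.
- **Silence.** No analysis set, missing-data rule, expected dropout or use of the interim ratings is stated.

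**The concern.** A percentage change and a signed-rank test on paired values can be computed only for people who have both values. With no other rule in the plan, the default is a completer analysis. Someone who leaves in week 7 with six or seven weekly ratings adds nothing to the estimate, and their response status at 1 month cannot be scored.

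Some of the listed reasons for leaving are tied to doing badly. Worsening is also what the weekly ratings would record, so whether the last rating is missing plausibly depends on scores already seen. In that case completers look better than the group that started.

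The estimate matters more here than the p-value. Under Study objectives, the efficacy data are pilot data meant to prepare a randomised trial, and an inflated change or response rate would carry into its planning. In addition, only one follow-up time has a planned estimate, although the end of daily treatment (Day 28), the end of the taper assessments (Day 56) and Day 84 are all assessed.

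**Working it through.** **1. Count of ratings.** Baseline 1 + Days 7–28: 4 + Days 35–56: 4 + Day 84: 1 = 10. The planned analysis uses 2. That all ten are MADRS ratings is an inference: quality of life is assessed at each post-baseline visit, and the quality-of-life scale shares the MADRS time points.

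**2. The plan's own figure.** The sample size of 50 cannot be reproduced, because no alpha, power, SD or effect is given. It is used below as n.

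**3. Inputs to a simulation** (4,000 trials per scenario).
- From the documents: n = 50; the ten days above; means of 27.5 at baseline and 15.5 at the end, from the open-label home study described under Home Use of tDCS. True change = 15.5 − 27.5 = −12.0.
- Assumed: intermediate means of 19 at Day 28 and 16.5 at Day 56, linear between; SD 5 at baseline, rising to 9; correlation at a gap of w weeks of ρ + (1 − ρ)·0.8^w with ρ = 0.3 or 0.5, multiplied by 0.7 for pairs that include baseline; the 1-month follow-up is Day 84.
- Assumed dropout, with no return: logit(hazard per visit) = a + z. Here z is the standardised deviation of the last observed score (missing at random, MAR) or of the current unseen score (missing not at random, MNAR), or is dropped (missing completely at random, MCAR). The constant a sets the total missing.
- Estimators: mean change in completers; maximum-likelihood repeated-measures estimate with unstructured covariance.

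**4. Check of the set-up with no dropout.** SE = √[(5² + 9² − 2·r·5·9)/50].
- ρ = 0.3: r = 0.7·(0.3 + 0.7·0.8¹²) = 0.244, so SE = √(84.1/50) = 1.30 (simulated 1.29).
- ρ = 0.5: r = 0.7·(0.5 + 0.5·0.8¹²) = 0.374, so SE = √(72.3/50) = 1.20 (simulated 1.22).

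With complete data the two estimators coincide.

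**5. Results** (each cell: ρ = 0.3 / ρ = 0.5; SE in brackets).

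| Dropout | Missing | Completer mean change | Repeated-measures mean change | Median % change, completers | Median % change, full data |
|---|---|---|---|---|---|
| MCAR | 30% | −12.07 (1.57) / −12.00 (1.43) | −12.07 (1.55) / −11.99 (1.39) | −44.0 / −43.7 | −43.9 / −43.6 |
| MAR | 10% | −12.15 (1.36) / −12.25 (1.25) | −12.01 (1.36) / −12.00 (1.25) | −44.5 / −45.0 | −43.7 / −43.6 |
| MAR | 21% | −12.32 (1.47) / −12.53 (1.34) | −12.02 (1.48) / −12.03 (1.36) | −45.6 / −46.4 | −43.6 / −43.7 |
| MAR | 30–31% | −12.45 (1.56) / −12.76 (1.42) | −12.01 (1.64) / −12.02 (1.47) | −46.6 / −47.8 | −43.7 / −43.7 |
| MNAR | 21% | −12.56 (1.45) / −12.73 (1.33) | −12.35 (1.45) / −12.32 (1.33) | −46.3 / −47.1 | −43.7 / −43.8 |

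**6. Size of the bias under MAR.**
- Mean: from 12.15 − 12.0 = 0.15 to 12.76 − 12.0 = 0.76 points, or 1% to 6% of 12. The largest is 0.76/1.42 = 0.54 of a standard error.
- Median: from 44.5 − 43.7 = 0.8 to 47.8 − 43.7 = 4.1 percentage points.

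**7. Response rate.** A separate simulation (300 trials per scenario, same end means, final SD about 9, dropout depending on the last score) gives the following. Missing as failure = completer rate × fraction observed.
- 19% missing: completers 46.5%, full data 42.5%. Missing as failure: 46.5 × 0.81 = 37.7%. Errors +4.0 and −4.8 points.
- 28% missing: completers 48.8%, full data 42.2%. Missing as failure: 48.8 × 0.72 = 35.1%. Errors +6.6 and −7.1 points.

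In these runs the two rates bracket the full-data rate, and neither is right alone.

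**The case against.** **Precision.** A reader might infer that using all ratings makes the estimate more precise. The results do not support that as a general claim. The SE gain is zero with complete data and 1–3% under MCAR. Under MAR with about 30% missing the SE is larger (1.64 against 1.56; 1.47 against 1.42). Root-mean-square error at that level runs from slightly worse (1.62 to 1.64) to about 9% better (1.61 to 1.47). The case is about bias.

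**Dropout may be small.** The only comparable figure in the documents is 1 of 34 (2.9%) withdrawn for missed sessions in the cited home study. The bias would then be below the 0.15–0.25 points seen at 10%. This stands. That figure covers one reason for leaving, though, and this plan gives no expected rate.

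**Inference is not text.** A reader might take the exclusion of early leavers for a stated rule, or ten MADRS ratings and Day 84 for stated facts. The exclusion follows from the paired method and the absence of any other rule. Someone whose stimulation stops might still be rated; the plan does not say. Day 84 is the natural reading, since it closes the four-week follow-up. But the cited study counted its month from the end of acute treatment, and daily treatment here ends on Day 28, so Day 56 is possible. The same point would then apply to Day 56, but the figures above would not carry over.

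**Different quantity.** A repeated-measures model estimates mean change, not median percentage change. This stands, and is why it should sit beside the planned summary. It does match the outcome as worded in Statistical Methods and Analysis.

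**Model limits.** The model is unbiased only under MAR; some reasons for leaving may reflect deterioration that was never rated. An unstructured covariance over ten visits has 10 × 11/2 = 55 parameters, from 50 people.

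**Low stakes.** Efficacy is a secondary objective and significance is not sought. That limits the severity, but a study meant to supply effect sizes still needs the effect size right.

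**Conclusion.** The concern holds, at modest size. As written, the efficacy analysis uses two time points and leaves out anyone without the second. If leaving depends on earlier scores, it overstates mean improvement by about 0.15–0.8 MADRS points and median improvement by about 1–4 percentage points at 10–30% missing. A likelihood-based repeated-measures estimate removes the bias in the mean under MAR. Under MNAR it only reduces it, from 0.56–0.73 to 0.32–0.35 points at 21% missing. Under MCAR there is nothing to correct.

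These sizes rest on assumed SDs, correlations and dropout rates, on weekly MADRS and on Day 84 as the endpoint. A reader might also infer that counting every missing score as failure gives the correct response rate. In the runs above it replaces an upward error with a slightly larger downward one, so it should not be the single headline figure.

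**What to change.** 1. Keep the median percentage change and the signed-rank test, and state how many people they include.
2. Add a pre-specified likelihood-based repeated-measures estimate of mean MADRS change. Use all scheduled ratings from everyone who had at least one session, with visit as a category, a named covariance structure and a fallback if it does not converge. Give 95% confidence intervals at Days 28, 56 and 84.
3. State which study day is the 1-month follow-up, and confirm that MADRS is rated at each weekly assessment.
4. Report response and remission twice, among those observed and over all who started with missing counted as failure, and present the pair as a range.
5. State that the model relies on MAR, and make no general claim of better precision.

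Cost: SAP wording and a little more analysis. No new data are needed if MADRS is rated weekly as implied. The report will carry a mean change beside the planned median, and the effect size may look less favourable.

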## **Sample Size**

The samples size of 50 is well within the sample size of previous published studies.

## **Withdrawal and Stopping the study**

The criteria for discontinuing a participant's participation include the participant's request, as well as any unexpected life-threatening or potentially disabling event.

A study subject may be withdrawn from the study at any time if the study subject, the investigator, or the Sponsor feels that it is not in the study subject's best interest to continue.

All study subjects are free to withdraw from participation at any time, for any reason, specified or unspecified, and without prejudice.

Reasonable attempts will be made by the investigator to provide a reason for study subject withdrawals. The reason for the study subject's withdrawal from the study will be specified in the study subject's source documents.

## **Stimulation Stopping criteria**

Subject stimulation will be stopped if any of the following occur during the 8-week treatment period:

- Clinician impression of substantial worsening of medical condition
- If the study subject misses more than 10 stimulation visits.

Study subjects will be withdrawn from the study for the following:

- If the study subject is not compliant with the study procedures as determined by the investigator.
- If, in the investigator's opinion, it is not safe for the study subject to continue with participation in the study.
- If the study subject is withdrawn from the study, the subjects treating psychiatrist will be notified so that arrangements can be made for continued treatment of his/her MDD.
- The study team will be notified by email immediately if the subject reports any adverse events during any tDCS stimulation session, and immediate follow up will occur.
- Any adverse events that take place during testing will be reported to the PI ([name]) and recorded in the database. Drs. [name], [name] and [name] will have primary responsibility for monitoring participant safety in the trial. The investigators will be responsible for reviewing each adverse event in a timely fashion and preparing a summary report for submission to the IRB.

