### **Study objectives:**

**Primary objective:** Demonstrate that remote tDCS sessions applied by a caregiver are feasible, complied and adhered to, and are safe in individuals with severe depression

**Secondary objective:** Gather pilot data on the potential of home-based tDCS to induce clinically meaningful improvements in the severity of depression in individuals who would otherwise be offered rTMS or ECT treatment.

The ultimate goal of this work is to prepare the path for a subsequent randomized clinical trial to assess the antidepressant therapeutic efficacy of home-based tDCS. We thus propose a study of tele-health supervised, caregiver-delivered, home-based tDCS for antidepressant treatment of patients with a medication-resistant depression episode of uni- or bi-polar Major Depression who would otherwise qualify for rTMS or ECT.

Specifically, in the present protocol we seek to offer participation to:

- Patients with medication-resistant MDD who have undergone rTMS or ECT and responded to it but whose benefit has lapsed, and they need repeat a rTMS or ECT course that they cannot access
- Patients with medication-resistant MDD who are undergoing rTMS or ECT and responding, but cannot continue to get the rTMS or ECT course due to COVID-19 pandemic-related regulations or other access concerns
- Patients with medication-resistant MDD who are referred to rTMS or ECT and are found well qualified but cannot access rTMS or ECT due to COVID-19 pandemic-related regulations or other access concerns.

The benefits of this project address a present need due to the COVID-19 pandemic, but also go beyond the present situation and address a larger, pre-existing need.

Across all these potential groups of participants, prospective participants will:

1. Need to have a primary psychiatrist who agrees to their participation in the study and is willing to continue to follow the patient and work collaboratively with the study team
2. Need to be assessed by their primary psychiatrist to be stable enough to be able to remain at home and participate in the present study without undue risk to their safety
3. Need to be living with an adult willing and capable to provide oversight and learn to deliver the home-based tDCS
4. Have the capability to connect with the study team for daily supervision of the intervention sessions and close safety monitoring, and be willing to commit to doing so

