In the setting of depression, Clayton et al., (2018) reported a case of one patient with comorbid multiple sclerosis and recurrent depressive episodes who received a course of remotely supervised tDCS following ECT treatment. Fatigue and mood ratings improved. More recently, Alonzo et al. (2019) completed a proof-of-principle, open-label trial in 34 participants who were taught to self-administer 20–28 tDCS sessions (2 mA, 30 min, F3-anode and F8-cathode montage according to 10–20 EEG placement) over 4 weeks followed by a taper phase of 4 sessions 1 week apart. Participants were initially monitored via video link for a few days, and then through completion of an online treatment diary. Participants met criteria for a diagnosis of MDD according to the DSM-IV-TR, as determined via an interview with a study psychiatrist, and confirmed with the Mini International Neuropsychiatric Interview (MINI; Version 5.0.0) (Sheehan et al., 1998). Inclusion criteria included a current major depressive episode of at least four weeks duration as part of a uni- or bipolar depression; and a score of at least 20 on the Montgomery–Asberg Depression Rating Scale (MADRS) at trial entry. Exclusion criteria were any DSM-IV-TR psychotic disorder; drug or alcohol abuse or dependence in the preceding 3 months; concurrent benzodiazepine medication; high suicide risk; history of clinically defined neurological disorder or insult; metal in the cranium or skull defects; skin lesions on the scalp at the proposed electrode sites; and pregnancy. Participants on antidepressant medication were permitted to enter the trial provided the medication dose was unchanged for 4 weeks prior to trial entry and during the acute treatment phase of the study. One participant was withdrawn from the study due to too many missed sessions. The remaining 33 participants completed 93% of the scheduled sessions in the initial 4-week phase. Ten of thirteen participants (77%) who qualified for the maintenance phase opted to continue. Mood improved significantly from baseline (27.5 on MADRS) to 1 month after the end of acute treatment (MADRS 15.5;  $p < 0.001$ ). Side effects reported across a total of 1,149 sessions were minimal, primarily mild to moderate tingling or burning/heat sensation during stimulation and redness at the electrode sites. This study provides clear, initial evidence that home-based, remotely supervised tDCS treatment is feasible for depressed patients and offers a potentially effective intervention.

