Daily sessions (28 daily sessions): The device will be used to apply 20 minutes of tDCS to the participant with MDD's scalp in each of 28 daily sessions.

Thereafter, participants with MDD will undergo a taper phase of an additional 9 sessions of tDCS applied in progressively decreasing frequency until day #60 of the study as follows:

- (1) First taper phase: three 30 minutes tDCS sessions applied every other day;
- (2) Second taper phase: three 30 minutes tDCS sessions applied one every third day;
- (3) Third and final taper phase: three final 30 minutes tDCS sessions applied one every fourth day.

The study team will predetermine, with the participant team, their most convenient two hour window for the home administration. During remote tDCS administration, the study team will be notified electronically by email when the tDCS session has been started and also when it has been completed, or if the tDCS session was aborted, or not completed during the predetermined two hour window.

The device will contain a sequence of simplified screen prompts for the participant,. To move to the next screen the participant will press a circle on the screen to continue (or to stop)

For example:

1. Hello
2. Battery status is GOOD
3. Today is Monday (date) It is now ( ) o'clock
4. Wear the Cap

5. Check the electrodes - 1 green is in the 1 green hole and secure, 2 yellow is in the 2 yellow hole and secure.
6. Are you ready for your 30 minutes session? If yes, press continue
7. Session has started, please stay in place until session is over [clock appears on screen to count down the minutes]
8. Session has ended, please stay in place while the device powers off.
9. Session is now completed! You may turn off the tablet, and remove the cap and electrodes

Daily sessions (28 daily sessions): The device will contain a block that will only allow one session to be administered within a 24 hour period. If a session is started and aborted, the participant will not be able to administer a new session until the next day, 24 hours later.

During the taper phase - the device block will only allow:

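### Non-compliance requires withdrawal from a study whose primary objective includes compliance, and no assessment is planned afterwards, so feasibility may look better than it is and the MADRS result may be biased in an unknown direction

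*Combined protocol and SAP*

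**What the plan says.** Under Study objectives, the primary objective is: "Demonstrate that remote tDCS sessions applied by a caregiver are feasible, complied and adhered to, and are safe in individuals with severe depression".

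Stimulation Stopping criteria contains two lists. The first stops stimulation during the 8-week treatment period, on substantial clinical worsening or on this condition: "If the study subject misses more than 10 stimulation visits". The second opens with "Study subjects will be withdrawn from the study for the following", and its first entry is "If the study subject is not compliant with the study procedures as determined by the investigator". The second list is mandatory in wording, rests on the investigator's judgement, and concerns the study as a whole.

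Statistical Methods and Analysis evaluates feasibility and tolerability by the reported number of aborted sessions. It names as primary outcome the "change in the observer rated MADRS score from baseline to the 1-month follow-up". The Statistics section makes this the median percentage change across subjects. CogState testing is an additional safety outcome, and the Visits table places a cognitive assessment at the final contact on Day 84.

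For a withdrawn participant, the plan records the reason in source documents and notifies the treating psychiatrist. It provides no later assessment, analysis set, missing-data rule, or rule that counts a withdrawal as a feasibility failure.

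**The concern.** Non-compliance is a negative result on the primary objective. In this plan it is also an event that ends observation, so the loss of data is tied to the quantity being measured.

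Three results are exposed:

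- **Feasibility.** A pair that aborts many sessions stops adding to the aborted-session count once it is withdrawn. Its missed sessions and its withdrawal are not part of the named measure at all.
- **MADRS.** The outcome needs a value at the 1-month follow-up. A participant withdrawn earlier is not scheduled to provide one, and without a missing-data rule the likely default is an analysis of those who have it.
- **Safety.** The final cognitive assessment is lost for the same participants.

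The study is meant to prepare a randomised trial. Adherence and retention over everyone who starts are among the main things that trial will need from it.

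**Working it through.** **Inputs from the documents.** There are 28 daily sessions and 9 taper sessions (Visits), a sample size of 50 (Sample Size), and a stimulation stop after more than 10 missed visits (Stimulation Stopping criteria). In the cited open-label home trial (Home Use of tDCS), 1 of 34 participants was withdrawn for too many missed sessions, and then: "The remaining 33 participants completed 93% of the scheduled sessions in the initial 4-week phase". The cited individual-patient meta-analysis gives 30.9% response on active tDCS (tDCS and Depression).

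**Assumptions.** The plan gives no withdrawal rate, so the number withdrawn, *w*, is varied. Withdrawn pairs are taken to have completed 0% to 70% of planned sessions; missing 11 of 37 leaves 26/37 = 70%. The 93% is borrowed from a 4-week phase and applied to all 37 sessions. The SD of percentage MADRS change is taken as 20 to 40 points. The sample size of 50 has no derivation to reproduce, and the point does not depend on it.

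**Step 1: schedule.** 28 + 9 = 37 sessions. A participant can miss 10/37 = 27.0% without triggering the stimulation stop. Anyone who goes through the full schedule without triggering it has therefore attended at least 27/37 = 73.0%.

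**Step 2: aborted-session count.** A pair that aborts 30% of sessions contributes 0.30 × 37 = 11.1 over the full schedule, but 0.30 × 10 = 3.0 if withdrawn after 10. Removing the pair lowers the count.

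**Step 3: the denominator in the cited trial.** Over all 34, adherence is (33 × 0.93 + *a*)/34, where *a* is the withdrawn participant's adherence. This gives 90.3% for *a* = 0 and 92.3% for *a* = 0.70, against the stated 93%.

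**Step 4: expected number here.** At the same rate, 50 × 1/34 = 1.5 withdrawals.

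**Step 5: all-enrolled figures for 50.**

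- Adherence = (0.93 × (50 − *w*) + *w* × *a*)/50, with *a* from 0 to 0.70.
- Response = (0.309 × (50 − *w*) + *r*)/50, with *r* from 0 (no withdrawn participant responds) to *w* (all respond).
- Median shift: if all withdrawn participants fall in the worse half, the all-enrolled median lies at the 25/(50 − *w*) quantile of the retained, counted from the best. Under normality the shift is z(25/(50 − *w*)) × SD. For *w* = 5, z(0.556) = 0.14, giving 2.8 to 5.6 points.

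| *w* | Adherence, all enrolled (93% in retained) | Response, all enrolled (30.9% in retained) | Median shift, points |
|---|---|---|---|
| 1 | 91.1–92.5% | 30.3–32.3% | 0.5–1.0 |
| 3 | 87.4–91.6% | 29.0–35.0% | 1.6–3.2 |
| 5 | 83.7–90.7% | 27.8–37.8% | 2.8–5.6 |
| 10 | 74.4–88.4% | 24.7–44.7% | 6.4–12.7 |

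Adherence moves one way only. Response can move either way. By symmetry, the median shifts by the same amount in the favourable direction if the withdrawn participants all fall in the better half.

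**The case against.** The strongest reply is that the plan nowhere excludes withdrawn participants from analysis. Session starts, completions, aborts and failures to complete within the window are notified electronically. Depression symptoms are assessed weekly through Day 56, and withdrawal reasons are recorded. All-enrolled adherence and withdrawal figures could be built from data already planned. This stands: the feasibility problem comes from the choice of measure and the missing denominator, not from lost session data. It does not restore a 1-month MADRS or a final cognitive assessment for someone no longer followed.

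A second reply is that the effect may be negligible. At 1 in 34, one or two participants are affected. This also stands as far as it goes. The present study has a longer schedule than the phase behind the 93% and an open-ended trigger, so its own rate is unknown.

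Third, a reader might infer that the missed-visit rule makes adherence high by construction. It does so only if those who trigger it are dropped from the denominator. The rule stops stimulation and is not listed as a reason for study withdrawal, so these participants may stay in follow-up. Nothing says whether they do, or whether the same person may also be judged non-compliant and withdrawn.

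Finally, study procedures include daily suicidality ratings, so non-compliance can mean more than missed sessions. Deleting the withdrawal rule outright would therefore reach into participant management, and that is not proposed here.

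**Conclusion.** The concern holds in this form: a mandatory, discretionary rule ends study participation on an event that belongs to the primary objective, and no follow-up, analysis set or missing-data rule limits the consequence. Feasibility may look better than it is, because the aborted-session count falls with each removed pair and ignores missed sessions and withdrawals.

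Two stronger readings are not supported. One is that the plan drops withdrawn participants from analysis; it is silent. The other is that the MADRS result is inflated. That requires non-compliant participants to do worse, which the documents do not show; with 5 of 50 withdrawn, all-enrolled response could be anywhere from 27.8% to 37.8% against 30.9% in those retained. The plan also says that a significant effect is not a defined goal, which limits the harm on that side.

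The size cannot be fixed from the documents. It is small at the cited rate and material at 5 to 10 withdrawals, counts that are assumptions. The 1-month follow-up is read here as the Day 84 assessment, which ends the four-week follow-up period; the plan does not expressly equate them.

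**What to change.** 1. Reconcile the stimulation-stopping and study-withdrawal lists. When stimulation or participation must end for safety is left to the sponsor.
2. State that ending stimulation, including for non-compliance, does not by itself end follow-up. The weekly phone assessments and the Day 84 assessment already scheduled continue unless the participant withdraws consent or declines them.
3. Over all enrolled pairs, report completed sessions out of 37, aborted sessions, missed sessions, and the number withdrawn for non-compliance. Count those withdrawn as adherence failures.
4. Analyse MADRS in all enrolled, with a missing 1-month value counted as non-response. For the median percentage change, prespecify a sensitivity analysis, for example placing missing values first in the worse half and then in the better half.
5. Say which visit is the 1-month follow-up.

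The cost is protocol wording, phone assessments for a few more participants, and reported figures that may be slightly less favourable. No new visit type is needed.
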